#### *Therapy satisfaction questionnaire (Patient) (Annex F)*

The questionnaire on the patient's satisfaction about the therapy (generic for both the group treated with Emoled and the control group) will be administered at the last visit, scheduled after 24 weeks, or at the control visit 4 weeks from the date of recovery. In this questionnaire, the patient is asked questions aimed at understanding whether the therapy (standard or with the addition of treatment with Emoled) has caused any kind of discomfort or has been well tolerated.

#### *Satisfaction, complexity and usefulness questionnaires (Operator) (Annex G)*

The operator satisfaction questionnaire (to be administered exclusively to staff belonging to Home Care) will be administered at the end of the study. It includes questions for the evaluation of the satisfaction of the healthcare personnel who used the device in use in this trial, with regard to its handling, functionality, effectiveness.

#### *Direct and indirect cost questionnaires (Patient, Caregiver and Operator) (Annexes H, I)*

Cost-specific questionnaires will be administered to patients and the main caregiver (if present) at the last visit with the aim of identifying the resources absorbed by the patients (and their caregivers) treated in the two approaches.

The consumption of resources will be assessed by collecting information aimed at quantifying direct health costs (visits, hospitalizations, access to the emergency room, use of medicines, etc.), direct non-health costs (informal care, transport costs and accommodation per visit, etc.) and indirect costs (loss of productivity of the patient and of the caregiver/s) and considering both the costs associated with adherence to treatment taking the last visit as "standard event", and the costs associated with complications and events relating the ulcer, that determined the need of treatments/examinations and/or medical evaluations. The principal investigator will also be given a questionnaire to determine the costs incurred by their structure for the management of patients with leg ulcers.

#### *Image acquisition*

A photographic image of the lesion will be collected during the 24 weeks of observation, or until healing and, eventually, the checkup to confirm the healing, to measure the area.

The photographic images will be acquired through the WoundViewer device (Omnidermal Biomedics srl – Torino IT), already present at the experimental centre.

The staff of the center will be trained in the use of this device and this training will be certified by the Omnidermal Biomedics srl company.

The WoundViewer device is able to store the photographic images per patient and also to calculate the wound area through a suitable analysis algorithm.

The value of the lesion area will be reported in the Image Collection Form (Annexes A, B, C) at the time of the visit.

#### *Bias - systematic errors*

The staff participating in the study will be trained on the correct use of the device and accessories, as well as on the correct execution of the clinical protocol and on the compilation of the associated forms. Although the sponsor does not participate in any way in the clinical trial, he will always remain at the team's disposal for any clarification regarding the correct management and use of the device under study.

#### **Number of experimental medical devices expected to be used**

Each investigator centre involved in the treatment will be provided with 5 EmoLED medical devices, distributed between the Diabetic Clinic and the Home Care.

#### **Timeframe of the study**

The study lasts 26 weeks (considering pre-screening, treatment period and final observation) with an approximate enrollment period of 18 months. However, the study will continue until the number of patients planned by this protocol is reached. For this reason, the overall duration of the study, from the enrollment of the first patient to the completion of the last, is estimated at 24 months

#### **Known or predictable factors that may compromise the results and their interpretation**

An incorrect recording of photographic images does not make it possible to determine the area of the lesion via software. This problem is tackled by providing precise instructions on the correct use of the tools available for the retrieval of images.

Discontinuity of patients regarding adherence to plantar offloading can affect recovery times. Before recruiting a patient, the doctor ensures that the patient is available to follow the prescribed therapy and to go to the clinic when required.

In case the patient misses a check-up visit, this can be regained within two days following the scheduled date. If this is not possible, the visit will not be carried out and the patient will be evaluated at the next visit. If the patient misses more than one visit, they will be excluded from the study (drop out).

Other reasons why patients will have to leave the study early are the lack of treatment, with EmoLED or with standard therapy, for more than four consecutive times, or for the lack of a quarter of home visits in total (unless non-treatment is provided for in this Protocol, such as in the case of suspension due to infection). Patients in which it is not possible to establish the exact date of recovery for various reasons, and patients who, in the opinion of the investigator, show a poor compliance with the therapeutic standards required by the study protocol, will also be excluded.

In such cases, the investigator will exclude patients from the study, recording on the data collection form, in addition to the date of exclusion, also the reasons why the patient was excluded.

The patient may, however, withdraw from the study at any time without having to give any explanation to the investigator (withdrawal of consent).

Following the exclusion or abandonment of the study by the patient, the data collection form is identified, scanned and stored.

If a patient withdraws from the study, the Principal Investigator records the event in the identification register and on the data collection form and stores it all.

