#### **Endpoints**

##### *Study primary endpoint*

The primary endpoint of the study will be the percentage of lesions considered healed (meaning as having a lasting and complete re-epithelialization) in the two groups at the twenty-fourth week of observation.

Healing must be confirmed by the Principal Investigator or their staff during an outpatient visit at the reference center participating in the study; the date of the recovery will in any case be indicated as the one of the first response, if it had occurred before the last visit to the reference center.

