In case, therefore, the lesion presents signs of infection as described above, the patient will interrupt their presence in the study and will be treated adequately. The patient can continue the study only if there is a remission of the symptoms of infection. The event will be reported in the appropriate section of the Data Collection Form.

The patient will be invited to a scheduled check-up at the referral center to assess the progress of the lesion, once every 30 days, or as needed.

The patient, if the wound healing occurs while being managed at home, will be invited to return for a check-up visit at the referral center within a week, to confirm the healing.

If at the conclusion of the participation of the patient in the clinical investigation, any additional treatments are required to those normally provided for the clinical condition considered in this study, the sponsor will cover the costs incurred for such treatments.

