#### *Registration of clinical data*

The data related to the evaluation of the study endpoints are acquired, for both groups, during the visits.

The parameters of the Data Collection Form, the questionnaires about quality of life and the questionnaire about the acceptability of the therapy are acquired during the outpatient visit at the reference centre and kept on paper for the clinical trial length, and conserved in both paper and digital form; the pictures of the lesion are acquired and kept in digital form, during the length of the clinical trial and afterwards.

The storage coding follows the patient recruitment code and acquisition timing.

During each visit, a picture of the lesion will be taken and analyzed so that the process of healing can be valued in a quantitative and qualitative way.

At each visit, data on the patient's perception of pain will also be collected.

The Quality of Life related questionnaires will be administered at the first visit and at the last visit, scheduled after 24 weeks, at the reference center. In particular, standard tools such as the generic EQ-5D questionnaire, validated in Italian, will be administered. Similarly, the questionnaire for the patient acceptance of the therapy (generic for both the group treated with EmoLED and the control group) will be administered at the

last visit, scheduled after 24 weeks, or on the date of recovery. The operator satisfaction questionnaire (to be administered exclusively to staff belonging to Home Care) will be administered at the end of the study.

*Data collection form (screening period) (Annex A)*

The collection of data relating to the Clinical Section includes the patient's identification code, date of birth, sex and characteristics of the lesion in question. There is also a space for any concomitant pathologies, any drug therapy (to be registered in terms of active substances). The last section is intended for recording the size of the wound.

*Data collection form (Research Center) (Annex B)*

The collection of data relating to the Clinical Section includes the patient identification code, date of birth, sex and characteristics of the lesion to be collected in the initial phase. There is also a space for any concomitant pathologies, any drug therapy (to be registered in terms of active substances), any notes.

The second part of the form is organized as a matrix where the row represents the measurable parameters for each time of observation (reported in column).

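### The two-day cancellation rule for missed visits does not exempt the week-24 visit, although a patient not yet confirmed healed has no scheduled visit after it

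*Protocol*

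**What the plan says.** The missed-visit rule is in the Protocol section Known or predictable factors that may compromise the results and their interpretation: "In case the patient misses a check-up visit, this can be regained within two days following the scheduled date". It continues: "If this is not possible, the visit will not be carried out and the patient will be evaluated at the next visit". A patient becomes a drop-out only after missing more than one visit. The rule makes no distinction between interim visits and the final one.

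The primary endpoint is the percentage of lesions healed "in the two groups at the twenty-fourth week of observation" (Study primary endpoint). The same section requires confirmation at the centre: "Healing must be confirmed by the Principal Investigator or their staff during an outpatient visit at the reference center participating in the study". Once healing is confirmed, "the date of the recovery will in any case be indicated as the one of the first response", if that came before the last centre visit.

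Registration of clinical data identifies week 24 as the last visit: "The Quality of Life related questionnaires will be administered at the first visit and at the last visit, scheduled after 24 weeks, at the reference" centre. The cost questionnaires are likewise given at the last visit (Direct and indirect cost questionnaires). Timeframe of the study ends participation at 26 weeks, including the two-week pre-screening. Under Management of missing data, a skipped visit in a patient who stays in the study is filled with the average of the two neighbouring visits or by LOCF.

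**The concern.** For an interim monthly visit the rule is workable, because another centre visit follows about a month later. For week 24, the fallback points to a visit that is not on the schedule. A patient who misses only this visit by more than two days is neither a drop-out nor unavailable, yet the rule says the visit is not carried out. An observation that could still be made is replaced by an imputed one. For the cost questionnaires it is replaced by nothing.

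An analysis plan cannot repair this. The rule governs visit conduct, and no analysis can recover an assessment that the protocol tells the site not to make.

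**Working it through.** No stated figure is to be reproduced here. The Protocol sets the sample size of 40 by recruitment capacity, and this point does not affect it. The check sets the visit rule against the visit schedule.

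**Is there a visit after week 24?** Pre-screening 2 + treatment 20 + observation 4 = 26 weeks, which is the stated length of the study. Week 24 after randomisation is therefore the end of participation, and no later visit is scheduled for a patient not confirmed healed.

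**The window.** Counting from the start of treatment, week 24 = 24 × 7 = day 168. Adding two days gives day 170.

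**Age of the carried-forward centre status.** Centre visits are every 30 days (Medical-surgical procedures and study follow up), also described as monthly (Study design).
- 30-day visits: days 30, 60, 90, 120, 150. Gap = 168 − 150 = 18 days.
- Four-weekly visits: the last one before week 24 is day 140. Gap = 168 − 140 = 28 days.

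**Which imputation applies?** The average of two neighbouring visits needs a visit on each side. The last visit has only one neighbour, so LOCF remains.

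**What LOCF does to each outcome:**
- *Healing already confirmed at the centre:* the status and date stand. Only the week-24 check that healing has lasted is lost.
- *Lesion still open at week 24:* carried forward as not healed, which is correct.
- *Lesion healed after the previous centre visit and confirmed through the home-healing check-up:* counted correctly.
- *Lesion healed after the previous centre visit and not confirmed:* carried forward as not healed, which is wrong. A home record may be more recent, but the endpoint requires confirmation at the centre.
- *Quality of life:* the questionnaires are given at the first and last visits, so LOCF carries the baseline value and the change becomes zero. This also feeds the QALY calculation. (Measurable parameters mentions quality-of-life data at the monthly visits, then repeats first and last only.)
- *Costs:* collected at the last visit only, so there is nothing to carry forward.

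**Size of one error.** 1/20 = 5 percentage points of an arm's healing rate.

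**The case against.** The strongest reply is that the sentence presupposes a next visit, so it describes interim checks and is simply silent on the last one. Centre visits may also take place as needed, and the centre's data form has a section for additional visits. A late examination is therefore not clearly forbidden. This stands in part: a reader might infer that the site must turn the patient away, and the text does not go that far. But it does say that the missed visit is not carried out, and it gives no authority for a late week-24 visit.

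Second, late healing has its own safeguard. Home nurses see the patient twice a week, and a patient whose wound heals at home "will be invited to return for a check-up visit at the referral center within a week, to confirm the healing". The questionnaire section also mentions a control visit four weeks after recovery. Healing between days 150 and 168 would put that visit on days 178 to 196, which fits poorly with a 26-week study and helps only patients already recognised as healed. The safeguard is real and narrows the primary-endpoint problem considerably. It does nothing for the quality-of-life and cost data of patients who have not healed.

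A reader might also infer that the two-day limit governs the healing-confirmation check-up, since both are called check-up visits. The document does not support this. That check-up is triggered by an event, has its own one-week timing, and has no scheduled date from which two days could run.

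Third, a missing visit already has a stated imputation rule. That is so, but LOCF is a poor substitute for an examination that could still be done, and it cannot supply costs.

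**Conclusion.** The point holds as a gap in a stated rule. Followed literally, the two-day rule removes the only scheduled week-24 observation of a patient who is still in the study and not yet confirmed healed, and with it the final quality-of-life and cost questionnaires.

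For the primary endpoint the effect is limited. Misclassification needs healing after the previous centre visit, no confirmation through the home-healing route, and a missed week-24 window, all in one patient. Each such patient moves the arm's healing rate by 5 percentage points. The Protocol gives no rate for any of these events, so the expected number cannot be derived. A reader might apply an assumed missed-visit rate to all 40 patients and treat the result as the chance of losing an endpoint. That would count missed visits rather than wrong outcomes, because confirmed healers keep their status and lesions still open are carried forward correctly.

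The quality-of-life and cost losses do not depend on healing in the final weeks. They affect any patient not yet confirmed healed who misses the window.

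The day counts assume that week 24 runs from the start of treatment and that monthly means every 30 or every 28 days. Absences of more than two days may be related to outcome in these patients, but the Protocol has no data on this and the conclusion does not rest on it.

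**What to change.** In Known or predictable factors, state that the two-day cancellation rule applies to interim monthly visits only. Add that the week-24 visit is still performed if late, within a wider window stated in advance, and recorded with its actual date. The sponsor should set the width; up to two weeks is one example.

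This takes about one sentence, adds no visits and changes no treatment. The downside is that a few week-24 assessments and questionnaires will be completed late, which the recorded date makes visible.

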#### *Study secondary endpoints*

1. Healing time (in which healing is represented by a lasting and complete re-epithelialization);
2. Reduction of the lesion surface in both arms, during the 20 weeks, measured in absolute terms (square centimeters) and as % of the initial size;
3. Quality of life (QoL), evaluated both with specific questionnaires (EuroQoL-5D) and generic questionnaires (Wound-QoL);
4. Perception of pain measured with a subjective analogue rating scale (VAS);
5. Assessment of the costs related to the two arms in the perspective of the National Health System, NHS (considering only direct health costs) and in the perspective of the Society (considering beyond direct health costs, direct non-health costs and indirect costs);
6. Patient's satisfaction with the EmoLED therapy, assessed by administering specific questionnaires;
7. Appreciation, complexity and usefulness of the EmoLED therapy by the operators assessed through the administration of specific questionnaires;
8. Security of treatment (number of Adverse Events in the two groups);
9. Evaluation of the cost-effectiveness of using EmoLED for the treatment of ulcers.

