### **Management of missing data**

As a pilot study based on a limited number of patients, the study will also include patients who do not complete the study according to the principle of "intention to treat" and the resulting missing data will be processed through the imputation technique of the missing data last observation carried forward-LOFC.

In case the patient does not leave the study but skips one or more control visits, the averages of the two adjacent visits or the last available data (LOCF) will be taken into consideration.

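### Randomised patients are excluded when their recovery date is uncertain, which selects on healing, and the other exclusion rules end follow-up before week-24 status is seen

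*Protocol*

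**What the plan says.** All references are to the Protocol.

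- **Known or predictable factors that may compromise the results and their interpretation.** The date rule covers "Patients in which it is not possible to establish the exact date of recovery for various reasons". The consequence is stated: "In such cases, the investigator will exclude patients from the study". The section also removes patients for more than four consecutive missed treatments, for missing a quarter of the home visits, and for poor compliance as judged by the investigator. On check-up visits it says: "If the patient misses more than one visit, they will be excluded from the study (drop out").
- **Study primary endpoint.** The endpoint is the percentage of lesions healed at week 24, with healing confirmed at the centre. The date is settled by convention: "the date of the recovery will in any case be indicated as the one of the first response". Statistical analysis compares the arms as healed or not healed.
- **Study secondary endpoints.** Healing time is a secondary endpoint, and it is the one that uses the date.
- **Medical-surgical procedures and study follow up.** A patient whose wound closes at home "will be invited to return for a check-up visit at the referral center within a week, to confirm the healing".
- **Management of missing data.** Here "the study will also include patients who do not complete the study according to the principle of" intention to treat, with LOCF. A separate rule (mean of the adjacent visits, or LOCF) applies thus: "In case the patient does not leave the study but skips one or more control visits".
- **Safety follow-up for subjects withdrawn.** Follow-up after exit is described only for the effects of incidents, not for wound status.

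**The concern.** There are two problems.

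First, the date rule is triggered by the outcome. Only a patient who has healed, or at the margin one whose healing is suspected but unconfirmed, can have an uncertain recovery date. A post-randomisation exclusion of that kind removes successes and leaves failures untouched. It also serves no purpose for the primary endpoint, which is a status at a fixed time.

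Second, the remaining exclusions treat poor attendance or adherence as a reason to stop observing the patient. Week-24 status could often still be obtained at a visit that is already scheduled. Once the patient has left, an earlier status stands in for it. If the ulcer was open at exit and closed later, the healed percentage in that arm is too low.

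The home nurses deliver the real or simulated treatment, and their data form records the group, so equal loss across arms cannot be taken for granted. The trial is described as a proof of concept whose results may inform the sample size of later studies, so a distorted healing rate would carry over into them.

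**Working it through.** **Inputs.** From the protocol: 40 patients, 20 per arm; and a combined drop-out and refusal figure of about 25%, used there for recruitment feasibility. The protocol gives no healing rate, effect size or loss by arm, so there is no stated result to reproduce on this point. The healing rates, exit rates and exit times below are all assumptions.

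**1. Date rule, one arm.** Take 10 healers of 20 (50%) and lose one.

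- Recorded healing kept: 10/20 = 50%.
- Coded not healed: (10 − 1)/20 = 45.0%.
- Removed from the analysis: (10 − 1)/(20 − 1) = 47.4%.

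Each affected patient therefore costs roughly 3 to 5 points, unless the recorded healing is kept.

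**2. Date rule, difference between arms.** Take 13 healers against 8 (65% vs 40%, gap 25 points), with *a* healers lost in the treated arm and *b* in control. Coded not healed, the gap is (13 − a)/20 − (8 − b)/20. Removed, it is (13 − a)/(20 − a) − (8 − b)/(20 − b).

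| Healers lost (treated, control) | Gap if coded not healed | Gap if removed |
|---|---|---|
| 1, 1 | 25.0 | 26.3 |
| 1, 0 | 20.0 | 23.2 |
| 0, 1 | 30.0 | 28.2 |

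The gap can move either way.

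**3. Early exit under the other rules.** Assume exponential healing with probability *p* of being healed by week 24, and a fraction *d* leaving at a time uniform over the 24 weeks.

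- LOCF healed proportion = (1 − d)p + d[1 − p/(−ln(1 − p))].
- Unknown coded not healed = (1 − d)p.

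The bracket is the chance of being healed already at exit: 0.217 for p = 0.40, 0.279 for p = 0.50 and 0.381 for p = 0.65.

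*Equal exit, d = 0.25, true 65% vs 40%.*

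- LOCF, treated: 0.75 × 0.65 + 0.25 × 0.381 = 58.3%.
- LOCF, control: 0.75 × 0.40 + 0.25 × 0.217 = 35.4%.
- LOCF gap: 22.8 points (from unrounded values) instead of 25.
- Not healed: 48.8% vs 30.0%, gap 18.8 points.

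*No true effect, 50% in both arms.* Equal exit gives no false gap. Exit of 35% in one arm and 15% in the other gives:

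- LOCF: 42.3% vs 46.7%, a false gap of 4.4 points from unrounded values.
- Not healed: 32.5% vs 42.5%, a false gap of 10.0 points.

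**4. Later exits.** The attendance and treatment criteria take time to accrue. With exits uniform from week 5 or week 8 to week 24, the LOCF gap in the equal-exit case becomes 23.6 or 23.9 points. The false gap under unequal exit falls to 3.3 or 2.7 points.

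**5. The two sections side by side.** One section makes a patient a drop-out at the second missed check-up. The other gives an imputation rule for a patient who stays in the study after skipping one check-up or several. A patient with two missed check-ups cannot fall under both. Neither section says whether a healed patient excluded for an uncertain date counts as healed, counts as not healed, or leaves the denominator.

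**The case against.** The best defence is that the two sections fit together: the first defines who drops out of the study, and the second keeps drop-outs in the analysis. On that reading a healer with an uncertain date but a recorded healing stays healed and nothing is lost. The removal figures apply only if the exclusion overrides the intention-to-treat statement, which no text says. This is a fair reading, but the protocol does not state it, and it cannot supply a week-24 status that nobody observed.

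The date rule should also trigger rarely, given twice-weekly home visits, a confirming visit within a week and a first-response convention. That is true, and it equally shows that the rule is not needed. Timing is not wholly irrelevant to status either: healing must be lasting, a control visit may be set four weeks after recovery, and closure near week 24 may be confirmed slightly later. None of this requires an exact date.

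The rates are assumed, the 25% is not a pure drop-out figure, and exits from week 0 overstate the loss. This stands: later exits shrink the effect without removing it. Blinding of patient and assessor makes a large imbalance less likely, although the home nurses know the allocation.

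Finally, per-protocol sets and sensitivity analyses usually belong in the SAP, and a primary imputation rule, LOCF, is already named. This also stands. But the exclusions and the end of follow-up are fixed in the protocol, and an SAP cannot undo them.

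**Conclusion.** The concern holds and should be fixed. The exact-date exclusion selects on the outcome and is unnecessary for the primary endpoint. The other exclusions replace an observable week-24 status with an imputed one.

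The size depends on the reading and on assumed rates. For the date rule it is nil if a recorded healing is kept, and otherwise about 3 to 5 points in the affected arm per healer lost. For early exit of 25% in both arms, the assumed 25-point gap falls to between 22.8 and 23.9 points with LOCF, depending on when exits begin, or to 18.8 points if unknown status is coded not healed (exit time does not matter there). Unequal exit of 35% vs 15% with no true effect produces a false gap of 2.7 to 4.4 points with LOCF, or 10.0 points if coded not healed.

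The direction of bias in the treatment difference cannot be determined from the protocol. Neither imputation rule is safe alone, so observing week-24 status is the better remedy.

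**What to change.** 1. Delete the exact-date exclusion for the primary analysis. A patient whose healing is confirmed at the centre counts as healed, however uncertain the date. Deal with the uncertainty only in the healing-time endpoint, using the first-response date or the interval between the last open and first closed assessment.
2. Record the other events in that section as protocol deviations, and continue outcome follow-up to the scheduled blinded week-24 centre assessment unless consent is withdrawn. Whether study treatment continues is a separate question, not addressed here.
3. State in both sections that all randomised patients stay in the primary analysis. Use the exclusion criteria at most to define a secondary per-protocol set.
4. Where week-24 status remains unknown, keep one pre-specified rule (LOCF is already named) and show the not-healed rule as a sensitivity analysis; the detail can sit in the SAP.
5. Reconcile the imputation rule for skipped control visits with drop-out at the second missed visit.

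The cost is protocol wording, plus attempting an already scheduled visit in patients who would otherwise have left. If the trial is under way, the protocol's own rules on deviations and amendments may require ethics approval, with suspension until a substantive amendment is approved. Keeping non-adherent patients may dilute the effect estimate slightly.
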